#### STUDY ASSESSMENTS AND TREATMENT SCHEDULE

| CMV surveillance                                 |                |           |        |              |          | X4             | X4   | X4        |            |            |
|--|----------------|-----------|--------|--------------|----------|----------------|--|-----------|------------|------------|
| Hematology   | Х              | X         |        | Х            | Х        | Х              | Х  | Х         | Х          | Х          |
| Chemistry  | Х              | Х         |        | Х            | Х        | Х              | Х  | Х         | Х          | Х          |
| PT/INR, PTT  | Х              |           |        |              |          |                |  |           |            |            |
| β 2 -Microglobulin                                | Х              |           |        |              |          |                |  |           |            |            |
| CT Imaging (neck, chest,
abdomen, pelvis)                 | X  | and asses | within | 14 da
and | ys prior |                | cle 3 assessment,
y 1 for Cycle 12
oint to confirm |           |            |            |
| Response assessment                              |                |           |        |              |          | X5             | X5   | X5        | X5         | X 5 |
| Serum Pregnancy Test   | X6             |           |        |              |          |                |  |           |            |            |
|  |                |           |        |              |          |                |  |           |            |            |
| FISH + IgHV  | Х              |           |        |              |          |                |  |           |            |            |
| Correlative Labs (PBMC)                          |                | Х         |        |              |          | X  | C7 only X                                    | Disease p | orogressio | n          |
| PKs    |                | Х         | Х      |              |          | Х              |  |           |            |            |
| Bone Marrow aspirate for
correlative studies  | Х              |           |        |              |          |                | X12  |           |            |            |
| PDs    |                | Х         |        |              |          | Х              |  |           |            |            |
| Umbralisib 800 mg  |                |           |        |              | Daily    | 7 Days 1 – 28  |  |           |            |            |
| Bone Marrow Biopsy                            | Х              |           |        |              |          |                | Х  |           |            |            |
| AE Assessment  |                | Х         |        | Х            | Х        | Х              | Х  | Х         |            |            |

 Visit days and all related assessments and testing have +/- 1 day window in Cycle 1.

 Unless otherwise noted (i.e. CT scans), visit days and all related assessments and testing have +/- 3 day window in Cycles 2 - 6.

 Unless otherwise noted (i.e. CT scans), visit days and all related assessments and testing have +/- 7 day window for Cycles > 6.

 Serum virology to include HBsAg, HBc antibody, HCV antibody, CMV IgG and CMV IgM. If HBc antibody is positive, the subject must be evaluated for the presence of HBV DNA by PCR - See Appendix C. If HCV antibody is positive, the subject must be evaluated for the presence of HCV RNA by PCR. If the subject is CMV IgM positive, the subject must be evaluated for the presence of CMV DNA by PCR. CMV surveillance by PCR every 3 cycles while receiving study treatment. In addition, a final CMV test by PCR should be done upon treatment discontinuation.

 Baseline CT scan within 30 days prior to Cycle 1, Day 1; then within 14 days prior to Cycle 4, Day 1 for Cycle 3 assessment, and within 14 days prior to Cycle 13, Day 1 for Cycle 12 assessment. Additional scans may be requested at the discretion of the investigator at any other time point to confirm progression (all scans +/-14 days). CT imaging should be performed at EOT visit if it hasn't been completed within past 30 days.

 Serum pregnancy test within 3 days prior to starting treatment on Cycle 1, Day 1 for women of childbearing potential.

 Peripheral Blood Mononuclear Cells (PBMC) – Peripheral blood sample to be obtained pre-dose on C1D1, C2D1, C4D1, C7D1, C13D1 and at the time of disease progression, which may occur at any time point including at the End of Treatment visit or the End of Study visit.

 PK samples (plasma) will be collected according to the schedule in Section 5.1.2. Additional PK samples may be collected outside of this schedule upon the occurrence of toxicity in order to correlate to plasma concentrations. PD samples (fresh peripheral blood) will be collected according to the schedule in Section 5.1.2. PBMCs will be isolated by Ficol centrifugation and B and T cell will be analyzed (post ex vivo stimulation) for phosphorylation of AKT.

-  An aspirate sample of 8-10 ml will be obtained at the time of each bone marrow biopsy- screening and the end of C12for correlative studies.
- Bone Marrow aspirate/biopsy performed at baseline and within 14 days following the last dose of Cycle 12 study drug. (Research lab Cycle 13

#### 5.1.1 LABORATORY ASSESSMENTS

Laboratory assessments will be collected as specified in the study assessments and treatment schema

#### 5.1.1 LOCAL LABORATORY ASSESSMENTS

1. Hematologic profile and serum chemistry to include through Cycle 6:

| Н          | ematologic Profile | e                         |
|------------|--------------------|---------------------------|
| Hematocrit | Neutrophils        | Platelet count            |
| Hemoglobin | Lymphocytes        | Absolute lymphocyte count |

| Erythrocyte count                    | Monocytes       | Leukocyte count           |
|--------------------------------------|-----------------|---------------------------|
| Basophils                            | Eosinophils     | Absolute neutrophil count |
|                                      | Serum Chemistry | ,                         |
| Albumin                              | Creatinine      | SGOT [AST]                |
| Alkaline phosphatase                 | Glucose         | SGPT [ALT]                |
| Bicarbonate (total CO 2 ) | LDH             | Sodium                    |
| BUN                                  | Magnesium       | Total bilirubin           |
| Calcium                              | Phosphorus      | Total protein             |
| Chloride                             | Potassium       | Uric acid                 |

Hematologic and Serum Chemistry windows as follows:

• Cycle 1: -1 day window

• Cycles 2 – 6: +/- 3 day window

2. After Cycle 6, required labs will include a standard CBC/differential and chemistry as below:

| Н                                    | ematologic Profile |                           |
|--------------------------------------|--------------------|---------------------------|
| Hematocrit                           | Neutrophils        | Platelet count            |
| Hemoglobin                           | Lymphocytes        | Absolute lymphocyte count |
| Erythrocyte count                    | Monocytes          | Leukocyte count           |
| Basophils                            | Eosinophils        | Absolute neutrophil count |
| 1                                    | Serum Chemistry    |                           |
| Albumin                              | Creatinine         | SGOT [AST]                |
| Alkaline phosphatase                 | Glucose            | SGPT [ALT]                |
| Bicarbonate (total CO 2 ) | LDH                | Total protein             |
| BUN                                  | Sodium             |                           |
| Calcium                              | Total bilirubin    |                           |
| Chloride                             | Potassium          |                           |

• Cycle 6: +/- 7 day window

3. Serum  $\beta$ -HCG test during screening for women of childbearing potential as outlined in Section 5, STUDY ASSESSMENTS AND TREATMENT SCHEDULE.

4. Serum Virology to include HBsAg, HBc antibody, HCV antibody, and CMV IgG and CMV IgM. If HBc antibody is positive, the subject must be evaluated for the presence of HBV DNA by

 Patients who discontinue study drug should have a follow up visit or telephone call to assess for AEs. This should be done 30 days (+/- 7 days) after the last dose of study drug. In addition, SAEs will be reported for 30 days after the last dose of study drug. (see section 10.4.3)

PCR. If HCV antibody is positive, the subject must be evaluated for the presence of HCV RNA by PCR. See Appendix C. If the subject is CMV IgM positive, the subject must be evaluated for the presence of CMV DNA by PCR. CMV surveillance by PCR every 3 cycles while receiving study treatment. In addition, a final CMV test by PCR should be done upon treatment discontinuation. See Section 5.

5. Baseline bone marrow aspirate/biopsy within 30 days prior to Cycle 1, Day 1, then follow Section 5 table, footnotes 11 and 12.

6.  $\beta_2$ -microglobulin at screening only.

7. Coagulation lab tests to include PT/INR and PTT.

8. Fluorescence in situ hybridization (FISH) of peripheral blood for 13q deletion, 11q deletion, 17p deletion, trisomy 12, t(11:14).

9. DNA sequencing for IgHV mutation status.

### 5.1.2 CENTRAL LABORATORY ASSESSMENTS

The PK parameters (including AUC  $_{(0-\infty)}$ , AUC  $_{(0-\tau)}$ , Cmax, tmax,  $\lambda_{z_{\prime}}$  and t1/2) of umbralisib will be assessed by analysis of umbralisib plasma concentrations.

PK blood (plasma) samples will be taken at the following timepoints.

| TABLE 1        | PHARMACOKINETIC ( | COLLECTION TIMES                         |
|----------------|-------------------|--|
| Visit          | Sched             | uled time point                          |
|                | Pre-do            | se                                       |
|                | 0.5 ho            | ur post dose (± 5 minutes)               |
| Cycle 1, Day 1 | 1 hour            | post dose (± 10 minutes)                 |
| Cycle 1, Day 1 | 2 hour            | s post dose (± 10 minutes)               |
|                | 4 hour            | s post dose (± 30 minutes)               |
|                | 6 hour            | s post dose (± 30 minutes)               |
| Cycle 1, Day 2 | Pre-do            | se, 24 hours post Day 1 dose (± 2 hours) |
|                | Pre-do            | se                                       |
| Cycle 2, Day 1 | 2 hour            | s post dose (± 10 minutes)               |
|                | 4 hour            | s post dose (± 30 minutes)               |
| Cycle 3, Day 1 | Pre-do            | se                                       |
| Cycle 4, Day 1 | Pre-do            | se                                       |
| Cycle 5, Day 1 | Pre-do            | se                                       |
| Cycle 6, Day 1 | Pre-do            | se                                       |

#### 5.1.3 PHARMACODYNAMICS

The analyses for pharmacodynamic biomarkers are exploratory and will not be used to guide treatment decisions.

[figure not shown]
#### PHARMACODYNAMIC COLLECTION TIMES

| Visit          | Scheduled time point (hours) |  |  |  |  |
|----------------|------------------------------|--|--|--|--|
|                | Pre-dose                     |  |  |  |  |
| Cycle 1, Day 1 | 2 Hours Post-dose            |  |  |  |  |
| Cycle I, Day I | 4 Hours Post-dose            |  |  |  |  |
|                | 6 Hours Post-dose            |  |  |  |  |
|                | Pre-dose                     |  |  |  |  |
| Cycle 2, Day 1 | 2 Hours Post-dose            |  |  |  |  |
|                | 4 Hours Post-dose            |  |  |  |  |
| Cycle 3, Day 1 | Pre-dose                     |  |  |  |  |
| Cycle 4, Day 1 | Pre-dose                     |  |  |  |  |
| Cycle 5, Day 1 | Pre-dose                     |  |  |  |  |
| Cycle 6, Day 1 | Pre-dose                     |  |  |  |  |
|                |                              |  |  |  |  |

# 5.1.4 CORRELATIVE STUDIES (EXPLORATORY OBJECTIVE)

Biological samples (Peripheral blood) will be collected at up to 6 time-points outlined in Section 5, STUDY ASSESSMENTS AND TREATMENT SCHEDULE. Each red top tube will be 10 ml of peripheral blood. Each green top tube will be 10 ml of peripheral blood. Bone Marrow aspirate will be collected at baseline and the end of Cycle 12. Each aspirate sample will be 8-10 ml of aspirate. As the correlative experiments are not the primary focus of the study and are more exploratory in nature, no sample size / power calculations were completed. Summary statistics will be used to summarize the quantitative measures (e.g., cytokine levels, expression levels) for the patients at the specified time-points with two-sample t-test use to determine if quantitative measurements differ between patients that respond and patients that do not respond at each time point. When assessing changes in quantitative measurements between time-points (e.g., pre and post treatment measurements) paired t-tests will be used. Longitudinal analysis with linear mixed models will also be used to look for statistical differences between the responders and non-responders using quantitative measurements at all time-points. Correlation between quantitative measurements will be assessed with Spearman correlation.

If correlative lab samples are drawn at a required time point and treatment is delayed, the sample may be retained. When the subject re-starts the cycle, the sample will be re-collected for continuity with other subject samples. The research lab will be notified of the event if the treatment is delayed.

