# 4. STUDY DESIGN

#### 4.1 OVERVIEW OF STUDY DESIGN

This study is designed as a Phase 2, single-center, single-arm trial to evaluate the ORR and PFS of umbralisib in treatment naïve CLL patients requiring therapy. Daily doses of oral umbralisib will be administered in the absence of disease progression, unacceptable toxicity, or withdrawal from treatment. Treatment cycles are 4 weeks, with the efficacy evaluations within 14 days prior to Cycle 4, Day 1 for Cycle 3 assessment, and within 14 days prior to Cycle 13, Day 1 for Cycle 12 assessment, and at any other time point to confirm progression. Patients who fail to achieve a partial or complete response to umbralisib at the Cycle 3 assessment will discontinue study treatment. At that time, patients- will be provided appropriate options to receive established frontline therapy. Patients who demonstrate a partial or complete response will be treated until disease progression, unacceptable toxicity, or the end of the study. Enrollment will be up to 35 patients.

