#### 4.2 REGISTRATION/ENROLLMENT

Following Screening, qualified patients will receive the following:

• Umbralisib 800 mg once daily

During the study period, all patients will be evaluated for response by CT or MRI within 14 days prior to Cycle 4, Day 1 for Cycle 3 assessment, and within 14 days prior to Cycle 13, Day 1 for Cycle 12 assessment, and at any other time point to confirm progression. Patients who fail to achieve a partial or complete response to umbralisib at the Cycle 3 assessment will discontinue study treatment. At that time, patients- will be provided appropriate options to receive established frontline therapy. Patients who demonstrate a partial or complete response will be treated until disease progression, unacceptable toxicity, or the end of the study.

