#### 4.4 DISCONTINUATION FROM STUDY TREATMENT

Patients will be discontinued from study treatment for any of the following reasons:

- Disease progression
- Failure to achieve a partial or complete response to umbralisib at the Cycle 3 assessment
- Intolerable toxicity related to study drug
- Patient requests to withdraw consent or discontinue treatment
- Pregnancy
- Inability of the patient to comply with study requirements
- Conditions requiring therapeutic intervention not permitted by the protocol
- Non-compliance/lost to follow-up
- Investigator discretion
- Discontinuation of the study

Patients who discontinue from study treatment prior to Cycle 12 (for reasons other than progressive disease) should continue to be followed for progression approximately every 3 months up until the time Cycle 12 would have occurred, then approximately every 6 months.

Patients who discontinue from study treatment after Cycle 12 for reasons other than disease progression should be followed for progression approximately every 6 months.

After withdrawal from protocol treatment, patients should be followed for AEs for 30 calendar days after their last dose of study drug. All new AEs occurring during this period must be reported and followed until resolution, unless, in the opinion of the investigator, these values are not likely to improve because of the underlying disease. In this case the investigators must record his or her reasoning for this decision in the patient's medical records.

All patients who have CTCAE Grade 3 or 4 laboratory abnormalities at the time of withdrawal should be followed until the laboratory values have returned to Grade 1 or 2, unless in the opinion of the investigator, it is not likely that these values are to improve because of the underlying disease. In this case, the investigator must record his or her reasoning for making this decision in the patient's medical records.

All patients that begin therapy outside of the scope of this protocol within 30 days of discontinuing umbralisib do not need to be followed for AEs, unless umbralisib is determined to be the direct cause of the AE in the opinion of the treating investigator. After 30 days from discontinuation of umbralisib, these AEs no longer need to be followed.

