#### 8.4 DEFINITIONS OF TUMOR RESPONSE AND PROGRESSION

Responses will be categorized as CR, PR, SD, or PD. Response criteria for this protocol will be per iwCLL 2018 criteria (see Appendix D). Response to therapy includes 2 groups of parameters that need to be documented. Group A assesses the lymphoid tumor load (CT) and constitutional symptoms; group B assesses the hematopoietic criteria. The hemataopoietic criteria will be evaluated using the lab testing on Cycle 4 Day 1 and Cycle 13 Day 1.

For the purpose of this study, the bone marrow biopsy response criterion will be calculated using the following formula:

Cellularity x % involvement of CLL= percent of response

If the reporting pathologist provides a range for B-cell or lymphocytic leukemia involvement (i.e.,80-85%), the higher number of the range will be used for the calculation.

The best overall response will be determined. The best overall response is the best response recorded from the start of treatment until disease/recurrence progression (taking as a reference for disease progression the smallest measurements recorded since treatment started). Where imaging data are available, these data will supersede physical examination data in determining tumor status.

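### Section 5.1.4 compares responders with non-responders at every time point, but the Cycle 3 stopping rule leaves essentially no non-responders to sample at C7D1, C13D1 or the end-of-Cycle-12 marrow

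*Combined protocol and SAP*

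**What the plan says.** Section 5.1.4 describes the correlative analysis. It plans a "two-sample t-test use to determine if quantitative measurements differ between patients that respond and patients that do not respond at each time point", and adds: "Longitudinal analysis with linear mixed models will also be used to look for statistical differences between the responders and non-responders", using the measurements from all time points. Paired t-tests are assigned to change between time points. The section calls the work exploratory and gives no power calculation.

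Footnote 7 of the Section 5 schedule sets the blood samples: "Peripheral blood sample to be obtained pre-dose on C1D1, C2D1, C4D1, C7D1, C13D1 and at the time of disease progression". For marrow, Section 5.1.4 says: "Bone Marrow aspirate will be collected at baseline and the end of Cycle 12".

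The treatment rule is in Section 4.1: "Patients who fail to achieve a partial or complete response to umbralisib at the Cycle 3 assessment will discontinue study treatment". Section 4.4 lists the same event as a reason for discontinuation, and Sections 4.2, 6.5, 8 and 9.7 repeat it. Imaging for that assessment falls "within 14 days prior to Cycle 4, Day 1 for Cycle 3 assessment". Section 8.4 adds the blood component: "The hemataopoietic criteria will be evaluated using the lab testing on Cycle 4 Day 1 and Cycle 13 Day 1".

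**The concern.** The variable that defines the two groups is also the variable that removes one of them from treatment. After Cycle 3 the patients still giving pre-dose samples are those who responded, so a test of responders against non-responders has nobody in its second arm. Section 5.1.4 does not limit the comparison to the visits before that point.

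Three things are at stake. The written plan promises tests that the design cannot deliver at the later visits. The mixed model receives late data from responders alone, apart from progression samples, so what it says about late group differences depends on how time is modelled, and the plan does not specify that. Finally, C4D1 is the last scheduled visit at which both groups could be compared on treatment, and no sentence ensures that the correlative tube is drawn from a patient who will not start Cycle 4. A tube that is not drawn cannot be recovered later.

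**Working it through.** **Availability of non-responders, visit by visit** (Section 5 schedule and footnotes 7, 9 and 10, read against Sections 4.1, 4.4 and 8.4)

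| Sample | Non-responders available? | Reason |
|---|---|---|
| C1D1, C2D1 | Yes | Before the Cycle 3 assessment |
| C4D1 | Likely, not secured | C4D1 laboratory tests feed the response call, but the correlative tube is defined as pre-dose and some patients will have no Cycle 4 dose |
| C7D1, C13D1 | None, subject to Section 8.5 | Off treatment; follow-up is for progression, with no correlative draw |
| End-of-Cycle-12 marrow | None, subject to Section 8.5 | Timed to the last Cycle 12 dose |
| Progression | Possible | Not tied to continued treatment, but taken at differing times |

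Of the five fixed blood visits, two support the comparison, one is uncertain and two do not. In the schedule, the correlative row for end of treatment and later visits is marked only for disease progression. A non-responder with stable disease therefore has no end-of-treatment tube either.

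**Group sizes**

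Inputs from Section 9.1: ORR 0.60 (null) and 0.80 (alternative), type I and type II error 0.10 each, 27 patients in stage 1, stop at 18 or fewer responses, 35 in total, success at 25 or more.

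1. *The plan's own figure.* Exact binomial calculation of this two-stage rule gives type I error 0.0965 and power 0.9003. A search returns 18/27 then 24/35 as the minimax design. The plan's design reproduces.
2. *Probability of stopping at 27.* P(X ≤ 18 | n = 27) is 0.816 at ORR 0.60 and 0.074 at ORR 0.80.
3. *Expected number enrolled*, 27 + 8 × (1 − probability of stopping): 27 + 8 × 0.184 = 28.5 at ORR 0.60, and 27 + 8 × 0.926 = 34.4 at ORR 0.80.
4. *Expected non-responders*, expected number × (1 − ORR): 28.47 × 0.40 = 11.4 at ORR 0.60, and 34.41 × 0.20 = 6.9 at ORR 0.80.

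Without the interim stop the figures would be 35 × 0.40 = 14 and 35 × 0.20 = 7. The first is too high as an expectation, because at ORR 0.60 the trial stops at 27 with probability 0.82. Given a stop, about 11.6 non-responders are expected; given continuation, about 10.3.

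**What the early visits can show**

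With 28 responders and 7 non-responders, a two-sided t-test at 0.05 (the Section 9.2 convention) has 80% power for a difference of about 1.22 SD (noncentral t). The chance of one or fewer non-responders among 35 at ORR 0.80 is 0.004. The early tests can be computed, but detect only large differences.

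**The case against.** The strongest reply is that little depends on this. The exploratory objectives in Section 2.1 are mostly alterations within patients, and Section 5.1.4 assigns paired tests to those. They remain computable in responders at every visit. A reader might infer that the trial's immune rationale fails without the group comparisons. Sections 1.3 and 2.1 do not support that, since neither frames the goal in terms of response groups. This part of the reply stands.

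A reader might also infer that C4D1 is empty for non-responders. That is not supported. Section 8.4 uses C4D1 laboratory tests for the hematopoietic criteria, and Appendix D needs blood parameters for a PR, so a C4D1 draw should generally occur before a patient is classified. C4D1 is also a listed correlative time point. What remains is narrower: nothing confirms that the correlative tube is taken when no Cycle 4 dose will follow.

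The late groups may also not be strictly empty. Section 8.5 keeps patients with lymphocytosis on drug until definitive progression, while Sections 4.1 and 4.4 stop anyone without PR or CR at Cycle 3. Section 8.4 has no category for partial response with lymphocytosis, which 7 of 20 CLL patients had in the phase 1 study described in Section 1.2.2.1. The documents do not say which passage governs, and they must be reconciled. This qualifies the finding without restoring a planned comparison group.

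Nor does the mixed model necessarily extrapolate. With time as a category, a late group contrast is simply not estimable. With time as a trend, it would rest largely on early visits. Section 5.1.4 does not say which is intended.

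**Conclusion.** The point holds as a mismatch between a stated exploratory analysis and the design. The responder versus non-responder t-test cannot be run at C7D1, C13D1 or on the end-of-Cycle-12 marrow, subject only to the unreconciled lymphocytosis patients. After C4D1, those patients aside, the mixed model has non-responder data only from progression samples. C4D1 itself is likely to be available but is not secured.

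The expected non-responder group is about 7 at ORR 0.80 and about 11 at ORR 0.60. These figures assume that the interim rule is applied as written, and ignore dropout for other reasons. The absence of late non-responders does not depend on the response rate. It rests on the Cycle 3 rule being followed and on non-responders having no off-treatment draws, and none are described. Classifying by best overall response (Section 8.4) does not refill the group, because a Cycle 3 responder remains a responder.

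The importance is low. The analysis is exploratory and unpowered, no primary, secondary or safety decision uses it, and the paired analyses survive.

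**What to change.** In Section 5.1.4:

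- Limit the responder versus non-responder t-tests and the mixed model to C1D1, C2D1 and C4D1, with groups defined by Cycle 3 response.
- Report C7D1, C13D1 and the end-of-Cycle-12 marrow as paired change within responders.

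In footnote 7 of the Section 5 schedule:

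- State that the C4D1 correlative tube is drawn from every patient together with the C4D1 response laboratory tests, whether or not Cycle 4 is started, and record the time since the last dose.

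A tube taken instead at an end-of-treatment visit would be a poor substitute. Non-responders would be sampled at an unspecified interval after their last dose and responders on drug, so response would be confounded with drug exposure.

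Separately, Section 8.5 and the Cycle 3 rule in Sections 4.1 and 4.4 must be reconciled, so that it is clear whether any patient can be a non-responder and remain on treatment.

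The cost is a wording change, one tube at a blood draw already planned, and fewer nominal comparisons. It should be settled before patients reach C4D1.
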